5.2 Exclusion Criteria

Patients will be excluded from the study if they meet **any** of the following criteria:

1. Prior therapy with EGFR TKI therapy
2. Greater than 2 lines of prior systemic therapy for metastatic non-small cell lung cancer.
3. Any cytotoxic chemotherapy or other anticancer drugs from previous treatment regimen or clinical study within 14 days of first dose of study drug.
4. Treatment with an investigational drug within 5 half-lives of the compound
5. Other active malignancy \leq 2 years prior to study enrollment. EXCEPTIONS: Non-melanotic skin cancer or carcinoma-in-situ of the cervix. NOTE: If there is a history of prior malignancy, patients must **not** be receiving other specific treatment (i.e. hormonal therapy) for their cancer
6. Prior radiotherapy \leq 14 days
7. Untreated symptomatic brain metastases (treated brain metastases are allowed provided $>$ 14 days have elapsed from completion of radiotherapy and patient is neurologically stable as assessed by treating physician).
8. Malabsorption syndrome, refractory nausea and vomiting, chronic gastrointestinal diseases, inability to swallow the formulated product or previous significant bowel resection that would preclude adequate absorption of osimertinib
9. Detection of concurrent *EGFR* mutation with exon 20 T790M, exon 19 deletion, exon 21 L858R mutation or exon 20 insertion. Patients with compound (also referred to as multiple mutations) will be excluded if the molecular testing includes one of these mutations
10. Active pregnancy or breast-feeding: Pregnant women are excluded from this study because the effects of osimertinib on the development of the fetus are unknown, and there is potential for teratogenic or abortifacient effects. Because there is an unknown but potential risk for adverse events in nursing infants secondary to treatment of the mother with osimertinib, breastfeeding should be discontinued if the mother is treated with these agents.
11. Grade \geq 2 blurred vision, conjunctivitis, corneal ulcer, dry eye, or keratitis
12. Men who intend to father children during the study or within 4 months afterward are excluded
13. Major surgery within 4 weeks of first dose of study drug.

14. Any unresolved toxicities from prior therapy greater than CTCAE grade 1 at the time of starting study treatment, with the exception of alopecia or neuropathy

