8.1 Screening

The following procedures and tests are to be performed within **28** days (unless otherwise specified) of study enrollment to confirm eligibility. Baseline and Cycle 1 Day 1 procedures may be completed on the same day, however, screening assessments to confirm eligibility **MUST** have already been determined. Refer to Table 4 for details.

1. Informed consent
2. Review of past medical history and previous therapies for NSCLC
3. Eligibility criteria review (Inclusion/exclusion)
4. Demography/Baseline characteristics, smoking history
5. A directed physical examination will be performed at the visit with vital signs including pulse, blood pressure, temperature, oxygen saturation, weight
6. Height
7. ECOG Performance status
8. Routine blood work (CBC, chemistries)
9. EKG in triplicate
10. Echocardiogram/Muga to assess LVEF
11. Pregnancy test if applicable
12. Tumor Histology
13. EGFR mutation status
14. Review of baseline sign/symptoms
15. Review of concomitant medications
16. Staging Disease assessment: Brain MRI, CT scan of chest and abdomen

8.2 On-Study Treatment Period: Day 1 of each cycle or as noted in Table 4

1. Review of interval medical history, concomitant medications and assessment of performance status
2. A directed physical examination will be performed at the visit with vital signs including pulse, blood pressure, temperature, oxygen saturation, weight
3. Laboratory: chemistry, and hematology
4. A repeat ECG may be performed at the discretion of the investigator or per institutional standard.
5. Echocardiogram/MUGA will be repeated if clinically indicated based on assessment of the investigator or per institutional standard
6. MRI of the brain to be performed with every 3 cycles starting with cycle 4 (cycles 4, 7, 10, 13 etc...) in patients with known brain metastases to assess for intracranial disease progression. Patients without brain metastases will undergo repeat brain imaging as clinically indicated.
7. Adverse event assessment
8. Review of study drug and diary
9. Pregnancy test (if applicable)

10. CT Chest/abdomen are done on day 1 of cycle 3, and then on cycles 5, 7, 9, 11, and 13 (every 2 cycles for the first year of study therapy). Then every 3 cycles (i.e. 16, 19, 22).

8.3 End of Study Treatment (30 days (+/- 3 days) after study therapy stops)

1. Review of interval medical history since the last visit and assessment of performance status

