All measurements should be taken and recorded in metric notation using a ruler, calipers, or a digital measurement tool. All baseline evaluations should be performed as closely as possible to the beginning of treatment and never more than 4 weeks before the beginning of the treatment.

The same method of assessment and the same technique should be used to characterize each identified and reported lesion at baseline and during follow-up. Imaging-based evaluation is preferred to evaluation by clinical examination unless the lesion(s) being

followed cannot be imaged but are assessable by clinical exam.

Clinical lesions. Clinical lesions will only be considered measurable when they are superficial (*e.g.*, skin nodules and palpable lymph nodes) and ≥ 10 mm in diameter as assessed using calipers (*e.g.*, skin nodules). In the case of skin lesions, documentation by color photography, including a ruler to estimate the size of the lesion, is recommended.

Chest x-ray. Lesions on chest x-ray are acceptable as measurable lesions when they are clearly defined and surrounded by aerated lung; however, CT is preferable.

Conventional CT and MRI. This guideline has defined measurability of lesions on CT scan based on the assumption that CT thickness is 5mm or less. If CT scans have slice thickness greater than 5 mm, the minimum size of a measurable lesion should be twice the slice thickness. MRI is also acceptable in certain situations (*e.g.* for body scans).

Use of MRI remains a complex issue. MRI has excellent contrast, spatial, and temporal resolution; however, there are many image acquisition variables involved in MRI, which greatly impact image quality, lesion conspicuity, and measurement. Furthermore, the availability of MRI is variable globally. As with CT, if an MRI is performed, the technical specifications of the scanning sequences used should be optimized for the evaluation of the type and site of disease. Furthermore, as with CT, the modality used at follow-up should be the same as was used at baseline and the lesions should be measured/assessed on the same pulse sequence. It is beyond the scope of the RECIST guidelines to prescribe specific MRI pulse sequence parameters for all scanners, body parts, and diseases. Ideally, the same type of scanner should be used and the image acquisition protocol should be followed as closely as possible to prior scans. Body scans should be performed with breath-hold scanning techniques, if possible.

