Complete Response (CR): Disappearance of all target lesions. Any pathological lymph nodes (whether target or non-target) must have reduction in short axis to <10 mm.

Partial Response (PR): At least a 30% decrease in the sum of the diameters of target lesions, taking as reference the baseline sum diameters.

Progressive Disease (PD): At least a 20% increase in the sum of the diameters of target lesions, taking as reference the smallest sum on study (this includes the baseline sum if that is the smallest on study). In addition to the relative increase of 20%, the sum must also demonstrate an absolute increase of at least 5 mm. (Note: the appearance of one or more new lesions is also considered progressions).

Stable Disease (SD): Neither sufficient shrinkage to qualify for PR nor sufficient increase to qualify for PD, taking as reference the smallest sum diameters while on study.

Evaluation of Non-Target Lesions

Complete Response (CR): Disappearance of all non-target lesions and normalization of tumor marker level. All lymph nodes must be non-pathological in size (<10 mm short axis).

Note: If tumor markers are initially above the upper normal limit, they must normalize for a patient to be considered in complete clinical response.

Non-CR/Non-PD: Persistence of one or more non-target lesion(s) and/or maintenance of tumor marker level above the normal limits.

Progressive Disease (PD): Appearance of one or more new lesions and/or *unequivocal progression* of existing non-target lesions. *Unequivocal progression* should not normally trump target lesion status. It must be representative of overall disease status change, not a single lesion increase.

Although a clear progression of “non-target” lesions only is exceptional, the opinion of the treating physician should prevail in such circumstances, and the progression status should be confirmed at a later time by the review panel (or PI).

Evaluation of New Lesions

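### The baseline scan need not follow the last prior treatment and may precede its end by up to about 13 days, so shrinkage from that treatment can count towards a confirmed response

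*Combined protocol and SAP*

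**What the plan says.** Timing of the baseline scan is set in three places. Appendix 4 (Methods for Evaluation of Disease) wants baseline evaluations "as closely as possible to the beginning of treatment and never more than 4 weeks before the beginning of the treatment". Table 4, footnote 1, gives 28 days before Day 1 of study therapy. Section 8.1 lists the CT and brain MRI among procedures to be done within 28 "days (unless otherwise specified) of study enrollment to confirm eligibility". All three look forward to the start of the study; none mentions the end of earlier treatment.

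Prior treatment is limited in Section 5.2. Item 3 excludes "Any cytotoxic chemotherapy or other anticancer drugs from previous treatment regimen or clinical study within 14 days of first dose of study drug". Item 6 reads only "Prior radiotherapy \leq 14 days", with no date from which the 14 days are counted. Item 4 excludes "Treatment with an investigational drug within 5 half-lives of the compound". Item 2 excludes "Greater than 2 lines of prior systemic therapy for metastatic non-small cell lung cancer", so patients with one or two earlier lines are eligible. Neither Section 5.1 nor Section 5.2 requires progression on the most recent regimen.

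Appendix 4 defines partial response as "At least a 30% decrease in the sum of the diameters of target lesions, taking as reference the baseline sum diameters", confirmed at least 4 weeks later. Section 22.4.2 bases the efficacy decision on the count of confirmed responders.

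**The concern.** The scan window reaches back 28 days from the first dose, while the drug washout reaches back only 14. A previously treated patient can therefore be scanned while still receiving the earlier regimen. If that regimen goes on shrinking the tumour after the scan, the shrinkage is measured against the study baseline and credited to osimertinib.

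This matters because every response is referenced to that one baseline and there is no control arm in which carry-over would show. Other windows in the protocol do not have this mismatch: Section 5.1 takes eligibility laboratory values within 14 days, in line with the drug washout, and Section 5.2, item 13, bars major surgery for 4 weeks, in line with the scan window.

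**Working it through.** **1. The plan's own design figures.** Inputs from Section 22.4.2: stop if 3 or fewer respond among 17; not worth pursuing if 10 or fewer respond among 37; ORR 20% under the null and 40% under the alternative.

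- Early stopping at 20%: sum over x = 0 to 3 of C(17,x)·0.2^x·0.8^(17−x) = 0.5489.
- P(go) at ORR p: sum over x = 4 to 17 of P(X₁ = x)·P(Bin(20,p) ≥ 11 − x). At 20% this is 0.0948. At 40% it is 0.9033, so the type II error is 1 − 0.9033 = 0.0967.
- Expected size under the null: 17 + (1 − 0.5489)·20 = 26.02.

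All agree with the plan. The issue is what is counted as a response, not the sample size.

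**2. The timing gap.** Days are relative to the first dose.

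- Earliest baseline scan: −28 (Appendix 4; Table 4).
- Latest prior drug dose: −15, taking a dose on day −14 as inside the excluded 14 days.
- Overlap: 28 − 15 = 13 days (28 − 14 = 14 if a dose on day −14 is allowed).

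For radiotherapy the same 13 days follow if item 6 is counted to the first dose. If it is counted to a date e days before the first dose, the overlap falls to 13 − e.

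**3. What the gap can do to a partial response.** Let the sum of diameters fall by a fraction x between the baseline scan and Day 1, and by a fraction s after Day 1. Partial response needs (1 − x)(1 − s) ≤ 0.70, so x ≥ 1 − 0.70/(1 − s).

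| Fall after Day 1 (s) | Earlier fall needed (x) |
|---|---|
| 0% | 30.0% |
| 10% | 22.2% |
| 20% | 12.5% |
| 25% | 6.7% |

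Carry-over need not supply the whole 30%. It can move a patient who would otherwise be stable to partial response.

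The opposite case uses the same rule. If the sum grows by k before Day 1, the fall needed from Day 1 is 1 − 0.70/(1 + k): 33.3% for k = 5% and 36.4% for k = 10%. An early scan then makes response harder to reach.

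**4. Whether confirmation removes it.** CT is scheduled on Day 1 of cycles 3 and 5 (Table 4, footnote 9), with 28-day cycles (Section 9.1), so at +56 and +112. Ignoring the 7-day window, and with prior treatment ending at −15:

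- cycle 3 scan: 56 + 15 = 71 days after the last prior treatment;
- cycle 5 scan: 112 + 15 = 127 days;
- unscheduled confirmation 4 weeks after the cycle 3 scan: 84 + 15 = 99 days.

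Confirmation tests whether the reduction lasts. It uses the same baseline sum, so it does not separate earlier shrinkage from later shrinkage.

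These steps show what the rules allow. They say nothing about how often it would occur.

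**The case against.** The strongest reply is that the Appendix 4 sentence has two limbs. A scan at day −28 in a patient treated until day −15, with a treatment-free fortnight still to come, does not fit the limb that asks for a scan near the start of treatment. That stands as a mitigation, and such a scan cannot be said to satisfy the whole sentence. But the limb states a preference; the only firm limit is 4 weeks.

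Several further points stand:

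- Only previously treated patients are exposed, and the documents do not give their expected share.
- The 5-half-life rule shortens or removes the overlap for some investigational drugs.
- A response from carry-over alone would have to last 71 days and then 99 or 127 days after the earlier treatment, which is likely to be uncommon.
- Tumours may grow during the washout, which works against response.
- The enrollment reference in Section 8.1 does not widen the gap, because Appendix 4 caps the scan at 4 weeks before treatment in any case. That mismatch is editorial.

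A reader might infer that ORR is biased upwards, or that the type I error exceeds 0.10 because 0.0948 leaves little room. The documents support neither. They give no rate of early scanning or of carry-over, growth acts in the opposite direction, and the small margin is a property of the design whatever the baseline rule.

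A reader might also extend the point to target lesions in irradiated areas. Appendix 4 admits these explicitly outside bone. Continuing shrinkage after radiotherapy would raise ORR and residual scar would lower it, and nothing in the documents settles the direction. It is not part of this point.

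**Conclusion.** The gap is real. In previously treated patients the rules permit a baseline up to about 13 days before the end of earlier treatment, and neither the response definition nor confirmation corrects for it. The 13 days assume that the last dose falls on day −15 and, for radiotherapy, that item 6 is counted to the first dose.

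The effect on ORR cannot be sized from the documents, and its net direction is uncertain. What is established is a possible misattribution of response in a single-arm trial whose efficacy decision is 11 or more confirmed responders of 37. It would be too strong to say that ORR is the whole basis for going forward, since Section 1.2 also asks for an acceptable safety profile. The weight is minor to moderate, and the change is worth making as a cheap improvement.

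**What to change.** State in Table 4, Section 8.1 and Appendix 4 that the baseline CT and MRI must be taken after the last dose of prior anticancer therapy and the last radiotherapy fraction, within the existing window of 28 days before Day 1. Use Day 1 as the single reference date in all three places.

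The cost is wording in three places and an occasional repeat scan for a patient imaged before earlier treatment ended. Where the washout is counted to the first dose, it already leaves about 14 days in which to scan, so neither eligibility nor the 3/17, 10/37 design changes. Some carry-over can remain, because a scan on the day after the last dose would comply.

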25.5 APPENDIX 5: Standard Cockcroft and Gault Formula for Calculated Creatinine Clearance

Standard Cockcroft and Gault Formula for Calculated Creatinine Clearance

For serum creatinine concentration in mg/dL:

Creatinine clearance (CrCl) will be calculated using the Cockcroft-Gault equation as follows:

$$\text{CrCl (ml/min)} = \frac{(140 - \text{age}) \times (\text{actual weight in kg}) \times 0.85}{72 \times \text{serum creatinine (mg/dL)}}$$

For serum creatinine concentration in $\mu\text{mol/L}$:

$$\text{CrCl} = [(140 - \text{age}) \times (\text{wt in kg})] / [0.81 \times \text{serum creatinine (mol/L)}]$$

Females: Multiply the result $\times 0.85$

Units: age in years, weight in kilograms.

Source: Cockcroft DW, Gault MH. 1976. Prediction of creatinine clearance from serum creatinine.

Nephron 16:31-4.
